7 SCREENING AND ELIGIBILITY

Subjects must meet the following inclusion/exclusion criteria to be eligible for the study.

7.1 Inclusion Criteria:

- Myeloma eligibility criteria are the following:
 - Near complete remission (nCR) for ≥ 3 months defined as no measurable M-spike, and a positive serum immunofixation
 - For patients with a light chain only myeloma, they will be deemed to be in a CR if they meet criteria for CR by International Myeloma Working Group (IMWG) consensus criteria2016.
 - For patients with a light chain only myeloma that meet criteria for Very Good Partial Response (VGPR) by IMWG consensus criteria 2016 and are IFE –ve (negative serum immunofixation), they will be considered to be in a near complete remission (nCR).
 - Or complete remission (CR) (no measurable M-spike, immunofixation negative and bone marrow clonal plasma cells <5%)
 - NDMM or RMM in nCR or CR having completed a minimum of 6 cycles of a lenalidomide based regimen for a minimum of ≥ 3 months
 - NDMM or RMM a patients who have been off corticosteroids for ≥ 4 weeks
 - Patients with NDMM or RMM who have had autologous stem cell transplant are eligible, but must be ≥ 12 months from transplant
 - All patients must be MRD positive at 10^{-4} or greater by NGS sequencing at enrollment
- All patients must be currently taking Revlimid at screening.
- Age >18 years
- ECOG performance scores 0-2
- History of measurable serum or urine M protein or free light chains
- Life expectancy greater than 12 months
- Corrected serum calcium < 11 mg/dL, and no evidence of symptomatic hypercalcemia
- Serum creatinine < 2 mg/dl
- ANC $>1000/\mu\text{L}$
- Platelet $>100,000/\mu\text{L}$
- Total bilirubin $\leq 1.5 \times \text{ULN}$
- AST (SGOT) and ALT (SGPT) $\leq 3 \times \text{ULN}$.
- Ability to comprehend and have signed the informed consent.
- Have previously agreed to continue on maintenance therapy with lenalidomide concurrent with vaccine administration until disease progression, or clinical indication to cease therapy.
- All patients must be willing and able to comply with the requirements of the REMS® program as directed by their providers.
- All study participants will have been registered into the mandatory Revlimid REMS® program as per standard of care, prior to enrollment.
- Females of reproductive potential must adhere to the scheduled pregnancy testing as required in the Revlimid REMS® program.

- Females of childbearing potential (FCBP)† must have a negative serum or urine pregnancy test with a sensitivity of at least 50 mIU/mL within 10 – 14 days prior to starting lenalidomide with each cycle (prescriptions must be filled within 7 days) and must either commit to continued abstinence from heterosexual intercourse or begin TWO acceptable methods of birth control, one highly effective method and one additional effective method AT THE SAME TIME, at least 28 days before taking lenalidomide, as per standard of care. FCBP must also agree to ongoing pregnancy testing. Men must agree to use a latex condom during sexual contact with a FCBP even if they have had a successful vasectomy. See **Appendix 5: Risks of Fetal Exposure, Pregnancy Testing Guidelines and Acceptable Birth Control Methods**.
- Able to take prophylactic anticoagulation (aspirin 81 or 325 mg/daily or, for patients intolerant to ASA, warfarin or low molecular weight heparin).

† A female of childbearing potential is a sexually mature woman who: 1) has not undergone a hysterectomy or bilateral oophorectomy; or 2) has not been naturally postmenopausal for at least 24 consecutive months (i.e., has had menses at any time in the preceding 24 consecutive months).

7.2 Exclusion Criteria:

- Disease progression after stopping corticosteroids as defined as the appearance of a detectable serum or urine M-spike, or an absolute increase of >10 mg/dl between involved and unininvolved light chains, in the absence of measurable serum or urine M-protein.
- Patients who are MRD negative by NGS at screening.
- Patients with a known diagnosis of POEMS syndrome, plasma cell leukemia, CNS involvement, non-secretory myeloma and amyloidosis
- High-risk myeloma defined by presence of at least one of the following defining features on initial diagnostic, or most recent bone marrow biopsy:
 - High risk chromosomal translocations by FISH: t(4;14), t(14;16), t(14;20),
 - del(17p), del(1p), amplification 1q.;
 - MyPRS GEP-70 or SkylineDx high risk signature either from diagnosis or at time of registration for the study;
 - LDH > 300 U/L at diagnosis;
 - Relapse from prior therapy within 12 months.
- HIV disease, active infection requiring treatment with antibiotics, anti-fungal or anti-viral agents within 2 weeks of enrollment would be excluded from the study.
- History of a pre-existing malignancy other than myeloma within the last 5 years with exception of treated basal cell or squamous cell carcinoma of the skin, or carcinoma “in situ” of the uterus, cervix or breast.
- Patients who have participated in any clinical trial, within the last four weeks, which involved an investigational drug.
- Autoimmune disease requiring active treatment.
- Known contra-indication to any component of allogeneic myeloma vaccine
- History of an allogeneic transplant

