Patients on a Len-containing regimen (VRD, Rd, BiRD or R) that achieved and maintained a nCR for 4-6 months were eligible for the study. Patients continued only on single agent Len and received 4 GVAX vaccinations consisting of two allogeneic MM lines: H929, U266 admixed with K562 transduced to express GM-CSF as well as PCV. Patients received 3 monthly vaccines and a boost at 6 months. Immune monitoring was performed on BM samples obtained at baseline, 6 months and 1 year.

To date 32 patients have been screened. 17 patients initially in a nCR were ineligible for vaccination: 3 (18%) had disease progression, 7 (42%) entered into an IFE negative CR, and 7 (42%) maintained a nCR during the observation period but opted not to enroll. 15 patients have been enrolled and completed their vaccinations. Patient characteristics are shown in the Table. Of note, none possessed high-risk features by ISS or FISH. Median follow-up for the study is 34.0 months. Median progression free survival (PFS) of the cohort of vaccinated patients has not been reached whereas the PFS in the observation arm that remained on the multidrug Len-containing therapy was 17.9 months ($p<0.001$) (figure 2). Vaccination in the setting of a rising M-spike was less likely to induce a durable remission with a median PFS of 14.3 months ($p<0.003$) (figure 3). Laboratory analysis showed that the patients achieving a CR had greater expression of PD-1 on CD4 and CD8 cells at baseline in the BM. Furthermore, durable responses were associated with the development and persistence of MM-specific immunity.

Patient characteristics:

	Vaccination (n=15)	Observation (n=16)
Age	69 (55-81)	66 (40-83)

FISH (high risk)	0%	0%
ISS Stage III	2 (13%)	3 (19%)
IFE negative	0 (0%)	7 (42%)
Prior Therapies	1.8 (1-4)	1.8 (1-3)

[figure not shown]

Figure 2. GVAX significantly prolong PFS in patients in a nCR

[figure not shown]

Figure 3. Presence of Disease Reduces Vaccine Efficacy

Vaccination with a poly-antigenic approach such as GVAX in combination with lenalidomide induced immunomodulation in patients with minimal residual disease generates potent MM-specific immunity, and appears to significantly extend the PFS. The promising early clinical activity has led us to design a randomized phase II trial to further explore this approach as a means to maintaining durable clinical remissions.

4.5 K562/GMCSF vaccine:

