Most patients achieving a CR still go on to relapse¹⁴. However, the depth and duration of CR may play an important role in disease prognosis, and higher CR has been shown to correspond with improved survival. The potential benefit of tumor vaccine may be best seen in the setting of minimal residual disease (MRD), where tumor induced tolerogenic mechanisms may be less relevant, and may be an effective mechanism of achieving a deeper remission such as stringent CR when not already in stringent CR, or molecular CR.

We will study the effect of the tumor vaccine in patients achieving at least a near complete remission (nCR), as well as a complete remission (CR) with a lenalidomide based regimen. The goal of the study will be to improve the clinical responses in patients with near complete remission (nCR) or complete remission who are also minimal residual disease positive (MRD+), and to determine whether the allogeneic myeloma vaccine confers a PFS advantage upon patients treated with allogeneic myeloma vaccine in combination with lenalidomide (with or without Prevnar vaccine) as compared to a non-vaccine control arm with patients on lenalidomide alone. The effect of adding Prevnar to the allogeneic myeloma vaccine and lenalidomide combination will also be explored.

Since administration of corticosteroids can dampen immune responses, patients will discontinue dexamethasone or other steroids at least one month prior to receiving the first vaccine, and must not show evidence of progressive disease as defined by the International Uniform Response criteria⁴⁷, prior to being started on the trial. The adverse

effects and significant morbidity from long term use of corticosteroids are well described, and this trial will give us an excellent opportunity to explore novel treatment strategies in a 'steroid free' regimen with a goal to improve the depth of response and have a low toxicity profile.

The incorporation of the Prevnar vaccination in our earlier study had a dual purpose. We were able to measure the efficacy of the vaccine by examining both the humoral, as well as cellular responses to Prevnar; and we uncovered a potential therapeutic effect of Prevnar vaccine in our earlier study. Specifically, the ability of Prevnar to prime T cell responses targeting HB-EGF (heparin binding epidermal growth factor), a cell adhesion molecule expressed on a significant percentage of myeloma cells.^{22, 23}

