6.2.2 Vaccine Formulation

The cell lines used for the vaccine preparation were manufactured and released by the Cell Processing and Gene Therapy Facility, a cGMP compliant facility, at the Sidney Kimmel Comprehensive Cancer Center at Johns Hopkins.. The vaccine cells are irradiated prior to cryopreservation and stored frozen in the vapor phase of liquid nitrogen until the day of use. The details of production, irradiation, freezing, and preparation for administration have been discussed in detail in the Investigational New Drug (IND) submission. Equal numbers (5×10^7 each) of the myeloma cell lines H929 and U266 cells will be combined with the bystander cell line K562/GM-CSF (5×10^6) to prepare the vaccine. Vaccine cells frozen in an injectable formulation Pentaspan® (10% Pentastarch in 0.9% sodium chloride with 2% human serum albumin and 5% DMSO) will be thawed on the day of vaccination in a 37°C water bath, mixed, and then taken up into three labeled syringes prior to administration. The cells are kept at 2-8°C with gel packs until administration. Injections should be started within 60 minutes of the thaw. Myeloma vaccine placebo injections will be saline solutions and will be prepared by the CTL at Johns Hopkins SKCCC in accordance with standard policies in order to maintain blinding.

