6.4.15 Prohibited Concomitant Therapy

Concomitant use of other anti-cancer therapies, corticosteroids, G-CSF, including radiation, thalidomide, or other investigational agents is not permitted while subjects are receiving protocol therapy during the treatment phase of the study. Topical, ophthalmic and inhaled corticosteroids are excluded.

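### Section 7.2 does not exclude earlier recipients of this myeloma vaccine, so a pilot patient who qualifies can be randomised to placebo and dilute the primary comparison

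*Combined protocol and SAP*

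**What the plan says.** Section 7.2 has two criteria that bear on earlier vaccination. The first is the four-week trial gap: "Patients who have participated in any clinical trial, within the last four weeks, which involved an investigational drug". The second is "Known contra-indication to any component of allogeneic myeloma vaccine", which concerns tolerability and not previous receipt. Section 7.1 adds nothing on the subject.

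Section 6.4.15 states that "Concomitant use of other anti-cancer therapies, corticosteroids, G-CSF, including radiation, thalidomide, or other investigational agents is not permitted", but that rule applies while patients are on protocol therapy, not before entry.

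On the pilot, Section 4.4 reports that patients "received 4 GVAX vaccinations consisting of two allogeneic MM lines: H929, U266 admixed with K562 transduced to express GM-CSF as well as PCV", that "15 patients have been enrolled and completed their vaccinations", and that "durable responses were associated with the development and persistence of MM-specific immunity". Median PFS among the vaccinated had not been reached at a median follow-up of 34.0 months. Marrow immune monitoring was at baseline, 6 months and 1 year.

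The product in this trial is the same: Section 6.2.2 says that equal numbers "of the myeloma cell lines H929 and U266 cells will be combined with the bystander cell line K562/GM-CSF". Section 4.8 confirms that the vaccine-plus-Prevnar arm repeats the earlier composition.

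Randomisation (Section 6.1.1) is 1:1:1, stratified by nCR versus CR and by prior autologous transplant. Section 11.2 names no covariate, subgroup or sensitivity analysis for earlier vaccination.

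**The concern.** The primary analysis compares 18 placebo patients with 36 vaccinated patients, and it assumes that the placebo patients have not had the vaccine. The entry criteria do not secure this.

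The pilot course was three monthly doses and a boost at six months, which matches the first four doses here. A pilot patient allocated to placebo would therefore be a control who has already had the initial experimental course. One allocated to vaccine would receive a re-boost and not a first course.

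If any earlier effect persists, the control arm progresses more slowly than planned and the hazard ratio moves toward 1. In an arm of 18, each such patient is 1/18 = 5.6% of the control information.

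**Working it through.** **1. Does any other provision close the gap?** The four-week rule, the contra-indication rule, the on-treatment bar in 6.4.15, the stratification factors and the analysis section were read together. None does. The pilot population also overlaps this one: nCR, on lenalidomide, 0% high-risk FISH. Continued remission and MRD positivity are further conditions, so the number who could qualify lies somewhere from 0 to 15.

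**2. Reproduce the planned power.** Inputs from Section 11.1: 18 versus 36 patients; medians 18 and 42.8 months; two-sided alpha 0.10; accrual over 24 months; minimum follow-up 36 months; loss 1% per year. Exponential PFS is assumed.

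- Hazards per month: λc = ln2/18 = 0.0385; λv = ln2/42.8 = 0.0162; ratio 18/42.8 = 0.4206 (the plan gives 0.4199). Loss: γ = −ln(0.99)/12 = 0.00084.
- Event probability = λ/(λ+γ) × the average over u from 36 to 60 of [1 − exp(−(λ+γ)u)]. This gives 14.85 control events and 19.01 vaccine events, 33.9 in all.
- Wald check: SE = √(1/14.85 + 1/19.01) = 0.346; |ln 0.4206| = 0.866; 0.866/0.346 − 1.645 = 0.856; power = 80.4%.
- Simulated log-rank test, 30,000 trials: 80.6% (simulation error √(0.8 × 0.2/30,000) = 0.2 points).

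The stated 80% is reproduced. Other closed-form approximations run from 76.8% (Schoenfeld) to 82.8% (Freedman).

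**3. Put k earlier recipients in the control arm.** Neither k nor the degree of carry-over is in the documents; both are assumptions. Full carry-over gives those k controls the vaccine hazard throughout. Half carry-over multiplies the control hazard by √0.4206 = 0.649. All vaccine-arm patients keep the planned vaccine hazard.

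| k of 18 controls | Power, full carry-over | Power, half carry-over | Control median, full (months) | Control 2-year PFS, full |
|---|---|---|---|---|
| 0 | about 80% | about 80% | 18.0 | 39.7% |
| 1 | 76% | 79% | 18.7 | 41.2% |
| 2 | 71% | 76% | 19.5 | 42.8% |
| 3 | 66% | 73% | 20.4 | 44.4% |

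The control median solves (18−k)/18 × exp(−λc·t) + (k/18) × exp(−λv·t) = 0.5. Planned 2-year PFS on vaccine is exp(−24λv) = 67.8%. The 2-year difference under full carry-over therefore shrinks from 67.8 − 39.7 = 28.1 points to 67.8 − 44.4 = 23.4 points at k = 3.

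**4. How many would land in control?** If m earlier recipients enrol, m/3 are expected in the placebo arm. The chance of at least one is hypergeometric, 1 − C(54−m,18)/C(54,18): 33% for m = 1, 71% for m = 3 and 88% for m = 5. If all 15 enrolled, which the entry criteria make unlikely, five would be expected.

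**The case against.** The best reply is that the problem may never arise, and much of that reply stands.

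- A reader might infer that pilot patients meet every entry criterion. The documents do not show it. Section 4.4 does not give any individual's current remission, lenalidomide or MRD status, and Sections 7.1 and 7.2 add laboratory limits, gene-expression risk, LDH at diagnosis and relapse timing. Patients who progressed, or who became MRD negative, are out. The 15 are a ceiling, not a forecast.
- A reader might infer that the vaccine effect is known to last for years. Immune sampling stopped at one year. The unreached median comes from 15 non-randomised patients, and this trial re-doses annually. What the text supports is narrower: persistence well beyond four weeks is plausible on the protocol's own account.
- Full carry-over for the whole of follow-up is the severe end of the range, which is why half carry-over is shown beside it. Six affected controls would exceed the five expected even if the whole pilot cohort enrolled, so that scenario is not used.
- A reader might infer bias in favour of vaccine. Allocation is random, so no systematic bias of that kind follows.
- A reader might extend the point to non-study Prevnar during follow-up. Section 6.4.17 already requires the case report form to capture all concurrent drugs, and the Section 2 schedule lists concomitant therapy throughout.

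The Cox models in Section 11.2 could adjust for earlier vaccination, and the baseline medical history may reveal it. Neither provision mentions it, however, and adjustment in an 18-patient arm is a weak substitute for not enrolling such patients.

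**Conclusion.** The point holds as a gap in eligibility. The criteria allow a previous recipient of the same vaccine to be randomised to placebo, and a four-week interval cannot be relied on to remove an effect that the protocol ties to persisting immunity.

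Its actual size cannot be determined from the documents and may be nil. If one to three such patients were among the 18 controls, the loss would be roughly 4 to 14 points of power under full carry-over (80% to 76–66%) and 1 to 7 points under half (80% to 79–73%). These figures rest on exponential PFS, the planned hazard ratio, and the assumed counts and carry-over. The consequence is dilution toward no difference, with some chance imbalance in a small arm. It gives no ground for doubting a positive result. It is worth correcting because the remedy is so small.

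**What to change.** Add to Section 7.2: *Prior receipt at any time of the allogeneic myeloma GVAX vaccine or another GM-CSF-based myeloma vaccine.* The wider wording also covers the earlier myeloma trials at the institution described in Section 4.6, which combined K562/GM-CSF with autologous tumour.

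If any such patient is already enrolled, flag this as a baseline variable and add to Section 11.2 a sensitivity analysis of PFS that omits those patients.

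Optionally, record at baseline the date of any earlier pneumococcal conjugate vaccine. Section 4.8 says "we uncovered a potential therapeutic effect of Prevnar vaccine in our earlier study", and the with/without-Prevnar comparison is a secondary objective. This is an extra, not part of the main correction.

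The cost is one exclusion line and the loss of at most a few candidates. The sample size of 54 need not change. Roll-over under Section 14 is unaffected for controls who have not had such a vaccine.

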
Lenalidomide: Patients will continue on a stable dose of lenalidomide on days 1 – 21 of a 28 day cycle until progression
 
Allogeneic myeloma vaccine consisting of 3 cell lines:
 
H929 5×10^7 cells/ vaccine
 
U266 5×10^7 cells/ vaccine
 
K562/GM-CSF 5×10^6 cells/ vaccine
 
Prevnar-13 administered with each myeloma vaccine
	
Allogeneic myeloma vaccine consisting of 3 cell lines to be manufactured by Aduro Biotech, and dispensed by the Cell Therapy Lab (CTL) at Johns Hopkins Sidney Kimmel Comprehensive Cancer Center (SKCCC).
 
Myeloma vaccine placebo injections will be prepared by the CTL at Johns Hopkins SKCCC.
 
Prevnar, and Prevnar placebo, will be prepared by the Pharmacy and Investigational Drug Service (IDS) at the Johns Hopkins Hospital.
 
All placebo will be made with saline.
 
For study participants, lenalidomide will be administered as a commercial drug.

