2. SCHEDULE OF STUDY ASSESSMENTS*

Procedure	Screen/Baseline ⁹ (Cycle 1 D 1 (28 days before)	Cycle 1 D 14 (+/- 3 days)	Cycle 2 D 14(+/- 3 days)	Cycle 3 D 14(+/- 3 days)	Cycle 6 D 14(+/-3 days)	1 year (+/-7 days)/Off- Study	18 months (+/-7 days)/Off-Study	2 years (+/-7 days)/Off- Study	30 months (+/-7 days)/Off-Study	3 years (+/-7 days)/Off- Study
Informed Consent	X									
Eligibility	X									
Complete medical history	X									
Interval history and review of patient vaccine reaction diary ¹		X X X	X	X X	X X X	X	X	X X	X	X
Review of systems ¹	X	X X X	X X	X X	X X X	X X	X X	X X	X X	X
Confirm diagnosis and stage	X									
Performance Status (ECOG) ¹	X	X X X	X X	X X	X X X	X X	X X	X X	X X	X
Concomitant Therapy ¹	X	X X X	X X	X X	X X X	X X	X X	X X	X X	X
Myeloma Vaccine or placebo ²		X X X	X X	X X	X X X			X		X
Prevnar Vaccine or placebo ³		X X X	X X	X X	X X X			X		X
Research Blood ⁴	X				X X			X		X
Bone Marrow Aspiration & Biopsy ⁵	X				X X			X		X
Safety Assessments:										
Adverse event query	-	X X X	X X	X X	X X X	X X	X X	X X	X X	X
Physical Examination, vital signs, weight	X	X X X	X X	X X	X X X	X X	X X	X X	X X	X
CBC with differential	X	X X X	X X	X X	X X X	X X	X X	X X	X X	X
Comprehensive panel	X	X X X	X X	X X	X X X	X X	X X	X X	X X	X
Pregnancy Testing ^{6,7}	X ₆	X X X	X X	X X	X X X	X X	X X	X X	X X	X
Disease Measurements:										
Minimal Residual Disease (MRD) testing ⁸	X ₁₀				X X			X		X
Protein electrophoresis (serum and 24 hr urine) or M-spike quantification (serum and 24hr urine)	X	X X X	X X	X X	X X X	X X	X X	X X	X X	X
Free light chain assay	X	X X X	X X	X X	X X X	X X	X X	X X	X X	X
Quantitative Immunoglobulins	X	X X X	X X	X X	X X X	X X	X X	X X	X X	X
Immunofixation studies (serum and 24 hour urine)	X	X X X	X X	X X	X X X	X X	X X	X X	X X	X
Beta-2 microglobulin	X									
Assessment of response ¹	X	X X X	X X	X X	X X X	X X	X X	X X	X X	X

In addition to the regularly scheduled study visits, an unscheduled visit can occur at any time during the study. Investigators may also assess participants via telemedicine at any point the investigator, local health or government authorities and/or other Hopkins authorities deem it appropriate. In these cases, an assessment may not include a physical exam or samples collection. All efforts should be made to perform in person visits if possible. Source documents must be maintained for these remote visits and unscheduled

visits. The date for the visit and any data generated must be recorded on the appropriate CRF.

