6.1.1 Registration on Study and Randomization

[figure not shown]
At registration, patients will have the baseline evaluations listed in Sections 2 and 7. Once eligibility requirements are met, the patients will proceed to bone marrow biopsy with cytogenetics and FISH analysis, and/or GEP assessment via myPRS, if this information is not already available at diagnosis, or on recent testing. Randomization in a 1:1:1 fashion will occur after screening and eligibility requirements have been met, and bone marrow biopsy obtained if needed. The primary criteria for stratification will be:

- Near Complete Remission vs Complete Remission (nCR vCR)
- Prior autologous stem cell transplant vs no prior autologous stem cell transplant

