6.2.1 Administration Parameters

At time of enrollment all patients will be on a stable, standard dose of lenalidomide given on days 1 – 21 of a 28 day cycle.

The following parameters must be present for each dose of the vaccine to be administered:

- No systemic infections requiring treatment
- Hemoglobin > 8g/dL
- Platelets > 20,000
- ALT/AST < 3X upper limit of normal
- Patient must be receiving lenalidomide on the day of the vaccine
- Missed vaccine doses can be made up within 2 weeks of the missed dose, with a delay by an equal number of days for the next dose (and the remaining doses), for the first 4 vaccine doses (there will be a minimum of one month between doses).
- Vaccine doses that are missed beyond the 4th dose of vaccine, can be made up within 1 month of the original date of administration. Subsequent doses do not need to be delayed.

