6.3 PREVNAR-13®

Other names: Pneumococcal 13-Valent Conjugate Vaccine

Classification: Infectious vaccine

Supplier: Prevnar-13 will be purchased from Wyeth Pharmaceuticals.

Dosage:

Prevnar-13 will be administered at 0.5ml dose by intramuscular injection. This dose will thus contain serotypes 1, 3, 4, 5, 6A, 6B, 7F, 9V, 14, 18C, 19A, 19F, and 23F and approximately 20 μ g of CRM₁₉₇ carrier protein; and 0.125mg of aluminum phosphate.

Since the product is a suspension containing an adjuvant, shake vigorously immediately prior to use to obtain a uniform suspension in the vaccine container. The vaccine should not be used if it cannot be resuspended or if particulate matter or discoloration is found.

Storage:

Vaccine is to be stored refrigerated at 2°C to 8°C (36°F to 46°F). It should not be frozen.

Contraindications:

Hypersensitivity to any component of the vaccine, including diphtheria toxoid, is a contraindication to use of this vaccine.

Warnings:

Healthcare professionals should prescribe and/or administer this product with caution to patients with a possible history of latex sensitivity since the packaging contains dry natural rubber.

Precautions:

Prevnar® is for intramuscular use only. Prevnar SHOULD UNDER NO CIRCUMSTANCES BE ADMINISTERED INTRAVENOUSLY. The safety and immunogenicity for other routes of administration (e.g., subcutaneous) have not been evaluated.

64 LENALIDOMIDE:

[figure not shown]

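### The eligibility criteria do not exclude known Prevnar-13 hypersensitivity, although section 6.3 contraindicates it and one blinded arm in three receives the product

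*Combined protocol and SAP*

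**What the plan says.** Section 7 makes its two lists decisive: "Subjects must meet the following inclusion/exclusion criteria to be eligible for the study". Within section 7.2 the only item on vaccine contraindications is "Known contra-indication to any component of allogeneic myeloma vaccine".

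Section 6.3, the Prevnar-13 product section, states: "Hypersensitivity to any component of the vaccine, including diphtheria toxoid, is a contraindication to use of this vaccine".

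Section 6.1.1 places allocation directly after eligibility: "Randomization in a 1:1:1 fashion will occur after screening and eligibility requirements have been met". According to the synopsis and section 6.1, one arm receives the myeloma vaccine with Prevnar-13. The other two receive saline in the Prevnar slot at the same visits. The title describes the trial as double-blind.

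**The concern.** The protocol names a condition under which one of its randomised products must not be given, but does not make that condition a bar to entry. Screening by the written lists would pass a patient with a known diphtheria-toxoid allergy. Staff are blinded, so nobody in the clinic would know whether the next intramuscular injection was Prevnar-13 or saline.

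Two things are at stake. The first is avoidable exposure to a known allergen; section 11.3 itself counts hypersensitivity and anaphylactic reactions of Grade 3 or higher as unacceptable toxicities. The second is trial conduct. If the allergy is noticed only after allocation, the assigned injection may have to be withheld or replaced, or the blind broken, for a patient who is already randomised.

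**Working it through.** This is mainly a comparison of texts, with a little arithmetic.

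**1. Does the section 7.2 item already cover Prevnar-13?** It covers components of the allogeneic myeloma vaccine. Section 4.7 and the synopsis define that vaccine as three cell lines: H929, U266 and K562/GM-CSF. Section 6.2.2 gives its vehicle as "10% Pentastarch in 0.9% sodium chloride with 2% human serum albumin and 5% DMSO". Prevnar-13 has its own section (6.3), supplier, intramuscular route and placebo, and one arm receives the myeloma vaccine without it. It is therefore not a component, and the item does not reach it.

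**2. Does any other criterion cover it?** No item in section 7.1 or 7.2 mentions Prevnar-13, pneumococcal vaccine, diphtheria toxoid or vaccine allergy.

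**3. Is there a check before each dose?** Section 6.2.1 begins "The following parameters must be present for each dose of the vaccine to be administered". The list covers infection, haemoglobin, platelets, transaminases, current lenalidomide use and the timing of missed doses. It contains no allergy check.

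**4. Do the discontinuation rules help?** Section 6.2.3 stops treatment for intercurrent illness, unacceptable adverse events, withdrawal, or a change in condition. These rules act on treatment already under way, and an allergy known at entry is not a change.

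**5. Would the information be available?** Probably. The schedule in section 2 calls for a "Complete medical history" at screening. No criterion tells the person taking it that a Prevnar-13 allergy is disqualifying.

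**6. Chance of assignment.** Inputs: 54 patients, 18 per arm (synopsis), allocated 1:1:1 (section 6.1).
- Assigned to Prevnar-13: 18/54 = 1/3.
- Assigned to saline in the Prevnar slot: 36/54 = 2/3.

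**7. Scheduled exposure.** The section 6.1 schedule has 4 injections (cycles 1, 2, 3 and 6) and 3 more (months 12, 24 and 36): 4 + 3 = 7. Seven is a ceiling, because an unacceptable reaction would end treatment under section 6.2.3.

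**8. Power.** The concern does not depend on power. As a check on the plan's own figure, a log-rank simulation under the section 11.1 assumptions gave 81.1% against the stated 80%. The inputs were 18 versus 36 patients, hazard ratio 0.4199, two-sided 10% alpha, 24 months' accrual, 36 to 60 months' follow-up and 1% yearly loss, over 10,000 runs. Removing one or two vaccine-arm patients gave 80.2% and 79.8%. An exclusion applied before randomisation removes nobody from the target of 54.

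**The case against.** The strongest reply is that the safety rule already exists. Section 6.3 is operative protocol text and no other section permits dosing a patient it bars. The history is taken before allocation, so the facts should be known in time. Section 6.2.3 adds at least 30 minutes of observation after each vaccination. Harm requires a patient with a known allergy, a screener who does not act on it, assignment to one arm of three, and an injection given against section 6.3. On that view this is a consistency edit. Unblinding is also not inevitable, because the pharmacy service prepares both Prevnar and its placebo and could act without telling the clinic.

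Much of this stands. The event would be rare, and the 1/3 is a chance of assignment, not of injection or harm. No eligibility checklist or pharmacy order is among the documents, so actual screening practice cannot be judged. The reply does not close the gap in the text. Section 6.3 takes effect at dosing, after randomisation. Observation and stopping rules act later still. The pharmacy route is possible, but the protocol does not describe it.

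A second reply is that any component could be read to include Prevnar, because sections 4.4 and 4.8 describe the Phase I vaccine as given with it. Those passages concern the earlier regimen. The current product is defined without Prevnar-13, and the point of the three-arm design is to give the vaccine with and without it.

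**Conclusion.** The concern holds. Followed exactly, the eligibility rule admits a patient who may not receive one arm's product and randomises that patient under blind. Such a patient has a 1/3 chance of assignment to Prevnar-13, with at most seven scheduled injections. How often this would arise cannot be estimated, because the documents give no prevalence of the allergy.

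The conclusion rests on the protocol text alone and assumes that no unseen checklist supplies the missing criterion. It makes no claim about power, the analysis or comparability of the arms. The change should be made because it is cheap and because a reaction in a patient known to be allergic is avoidable.

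**What to change.** Extend the section 7.2 item so that it excludes a known contraindication to any component of either product, the allogeneic myeloma vaccine or Prevnar-13, and name hypersensitivity to diphtheria toxoid. Check it in every candidate before randomisation, since the arm is not known at that stage.

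The authors could also consider adding a screening question on latex sensitivity. Section 6.3 treats that as a caution only, so it need not be an exclusion.

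The cost is one line of text and the loss of the rare candidate with this allergy, including the 2/3 of such candidates who would have been assigned to an arm without Prevnar-13. The sample size, type I error rate and power are unchanged.
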